Tumor assessments will be performed at screening and approximately every 8 weeks starting at the end of cycle 2 for the first 6 months (cycles 2, 4, 6) and then every 12 weeks (cycles 9, 12, 15, etc.), or sooner if deemed necessary by the Investigator, and will continue until disease progression. A tumor assessment will be performed upon treatment discontinuation (End of Treatment visit) if the reason for discontinuation is other than disease progression and no tumor assessment was performed in the prior 8 weeks, or a tumor assessment is required for the confirmation of response to treatment. Subjects who discontinue treatment for reasons other than disease progression must continue tumor assessments until disease progression, withdrawal of subject's consent or initiation of another anticancer therapy. Determination of objective tumor response will be performed by the Investigator. However, tumor images may be de-identified of subject's personal information at the clinical sites and collected by the Sponsor or designee to undergo an external independent radiological review if the sponsor deems it necessary for the final assessment of the efficacy of the treatment. If an independent radiological review were to be conducted, reviewers would be blinded to Investigator's tumor response assessments. An independent review committee charter would be generated to provide the specific procedures that would be filed with IRB/ECs and regulatory authorities.

Subjects with a solitary site of disease who have experienced a response may be considered for surgical resection. Subjects with a Partial Response (PR) and residual disease after salvage surgery are eligible to continue on study therapy.

Upon disease progression, all subjects in the study cohort will be followed approximately every 12 weeks for survival and the use of subsequent therapy until either death or 12 months after accrual in the subject's study cohort has been completed, whichever occurs first. Information on survival and subsequent anticancer therapy may be collected by phone.

All subjects will be followed-up for safety during treatment and up to approximately 30 days (30 +/- 7 days) after treatment discontinuation or until immediately before the initiation of another anti-cancer therapy, whichever occurs first. Additional follow up may be implemented until the

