8.6 Definition of End of Study

For administrative and safety reporting purposes, the end of this clinical study is defined as 12 months from enrollment of the last enrolled study subject. If the last enrolled study subject discontinues treatment within 12 months of study enrollment, the End of Study will occur no earlier than the date of the last enrolled subject's safety follow-up assessment performed approximately 30 days after treatment discontinuation (or until initiation of another anti-cancer therapy). At the time of End of Study, provisions will be made to transition all remaining study subjects who demonstrate sustained clinical benefit beyond the end of the study to other means of continued treatment with tipifarnib, including appropriate safety monitoring, e.g. single patient treatment protocol. For subjects enrolled in France and who have evidence of clinical benefit, continuation of treatment with tipifarnib may only take place in the setting of a separate study protocol. For subjects enrolled in Germany and who have evidence of clinical benefit, continuation of treatment with tipifarnib may only take place in the setting of a clinical trial or hardship program ("compassionate use") per German Drug Law (AMG).

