9 TREATMENTS

Subjects will receive tipifarnib as monotherapy in this study. In the absence of unacceptable tipifarnib related emergent toxicity or disease progression, subjects may receive treatment with tipifarnib for up to 12 months at the discretion of the Investigator. Treatment beyond 12 months may continue upon agreement of the Investigator and the Sponsor. Kura Oncology, Inc. or its designee will provide the study site with a supply of tipifarnib sufficient for the completion of the study.

All study subjects will be also eligible to receive best supportive care (BSC) defined as any standard supportive measures that are not considered a primary treatment of the disease under study, including the use of growth factors (i.e. GCSF) or blood transfusions for myelosuppression. BSC will be provided by the study sites.

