The second 7-day schedule study was conducted in patients with relapsed/refractory AML (Kirschbaum 2011). Tipifarnib was administered bid on days 1–7 and days 15–21 of 28-day cycles at doses up to 1600 mg bid (Kirschbaum 2011). At the 400 mg bid dose level, a grade 5

hepatorenal failure occurred, potentially related to the study drug. There were no additional DLTs reported at 600, 800 or 1000 mg bid dose levels. At the 1200 mg bid dose level, a grade 3 creatinine elevation was seen in one patient out of 6 treated. At the 1400 mg bid dose level, one patient experienced a grade 4 hypotension and a rising grade 2 creatinine that were dose limiting, and a second patient had a rising grade 2 creatinine that resulted in treatment discontinuation and was therefore considered dose limiting. At the 1600 mg dose level, grade 3 liver function tests and a rising grade 2 creatinine were dose limiting, and in a second patient, a rapidly rising creatinine was seen and treatment stopped. As a result, the 1200 mg bid dose was established as the MTD and 7 additional patients treated. Sixteen patients were treated at the 1000 and 1200 mg dosing levels, with 3 of them experiencing complete responses. No formal responses were seen among patients treated at the lower dose levels.

Based on these data, the tipifarnib regimen to be investigated in the current study was modified to a starting dose of 900 mg, po, bid on days 1-7 and 15-21 of 28-day treatment cycles. Preliminary data from KO-TIP-001 indicate a tolerability that is broadly similar to the safety profile observed of other tipifarnib regimens in prior clinical studies which administered tipifarnib daily in a 21-day on, 7 days off treatment cycle schedule. The most common AES of tipifarnib including hematological events, gastrointestinal disturbances (nausea, vomiting and diarrhea) and fatigue have been monitorable and manageable with protocol defined assessments and management of toxicity guidance. Dose reduction to 600 mg has been able to reduce tipifarnib-related toxicity and several subjects have maintained their response and continued on treatment for over 1 year.

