10.9 Adverse Event Reporting Period

The adverse event reporting period for safety surveillance begins when the subject is included into the trial (date of first signature of informed consent) and continues through the trial's post-treatment follow-up period, defined as 30 days from the final administration of the trial treatment or immediately before initiation of any other anticancer therapy, whichever comes first.

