11.7 Post Treatment Follow up

Follow up visit(s) are required only for subjects who terminated treatment for reasons other than death or disease progression and should occur approximately every 8-12 weeks until disease progression or death, whichever occurs first. If the subject initiates a new anticancer therapy without evidence of disease progression by RECIST v1.1, tumor assessments should continue

until there is evidence of disease progression unless withdrawal of subject's consent to study procedures.

The assessments to be conducted at these visits are:

- Radiographic Imaging: to be performed if not done within the prior 8 weeks or if a tumor assessment is required for the confirmation of response.
 - o CT scan with a contrast agent is the preferred imaging method and the same technique should be used at baseline and post-treatment assessments.
 - o In subjects with HNSCC, CT scan coverage at screening should encompass scans of the neck (including the skull base), chest and abdomen (including the liver and adrenals). Any other areas of disease involvement should be scanned based on the subject's signs and symptoms.
 - o In subjects with other solid tumors, scan coverage should be appropriate to ensure that all areas of disease involvement are scanned.
- Assessments of AEs and concomitant medications may also be conducted if AEs were not resolved at the time of the End of Treatment visit.

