9.3. Other Efficacy Analyses

Per subject data on detail of tumor burden marker, and on subsequent therapy and survival status will be displayed in listings.

Waterfall figures and spider plots will illustrate best overall percent change in tumor burden (defined as sum of diameters) for the FAS population, the PP population and by subgroup.

An analysis of overall survival to estimate median overall survival time and corresponding 95% confidence interval and provide per subject summary of overall survival will be conducted. Overall survival will be defined as the time (in months) from first dose (Cycle 1 Day 1) to the occurrence of death due to any cause. In subjects without a death date, the OS will be censored on 1) the last date of survival status if alive, 2) a data analysis cutoff date for subjects with no survival status documentation, or 3) the date a subject withdraws consent or is lost to follow-up, if there is no additional information.

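### In cohorts that close before the study's last enrolment, survival follow-up past the cohort date depends on progression status, so the late part of the OS curve is biased upward if the data cutoff falls after that date.

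*Protocol*

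**What the plan says.** Survival follow-up opens at progression: "Upon disease progression, all subjects in the study cohort will be followed approximately every 12 weeks for survival" (Protocol 8.1). It runs "until either death or 12 months after accrual in the subject's study cohort has been completed, whichever occurs first". Protocol 10.1, Protocol 11.7.1 and SAP 4.1 repeat this. Call that end date C; each cohort has its own.

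Subjects without progression have no such date.

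- On treatment (Protocol 9): "Treatment beyond 12 months may continue upon agreement of the Investigator and the Sponsor". Scans continue to progression.
- Off treatment without progression (Protocol 11.7): visits "should occur approximately every 8-12 weeks until disease progression or death, whichever occurs first".
- The only outer limit is in Protocol 8.6: "the end of this clinical study is defined as 12 months from enrollment of the last enrolled study subject". This counts the whole study, not the cohort.

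SAP 9.3 defines OS from first dose to death from any cause. Subjects without a death date are censored on "the last date of survival status if alive" (rule 1), at the data cutoff if no survival status is documented (rule 2), or at withdrawal or loss to follow-up (rule 3). No OS cutoff common to a cohort is given. SAP 9 presents efficacy by cohort and by subgroup, and SAP 7.5 pools Cohort 2 Stage 2 with Cohort 3. SAP 14 records OS as an added analysis.

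**The concern.** Kaplan-Meier needs subjects who leave the risk set to have the same prognosis as those who stay. After C this fails by design. Subjects who progressed earlier have left. A subject who first progresses after C has no survival follow-up window remaining and is lost soon afterwards. Those still at risk have been selected for not having progressed. This happens even if every site follows the plan exactly and no data are missing.

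At stake is the tail of the OS curve, where durable benefit is read, and the median if it is long. The error always favours the drug and cannot be seen on the plot.

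**Working it through.** **No figure to reproduce.** The documents give no OS rate, median, event count, cohort closing date or accrual length. Everything numerical below rests on assumptions.

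**Where bias can arise.** A subject enrolled u months before the cohort's accrual closes reaches C at 12 + u months from first dose.

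- Since u ≥ 0, nobody reaches C before month 12, so OS up to 12 months is unaffected.
- Let the gap be End of Study minus C, that is, the study's last enrolment minus the cohort's last enrolment. In the cohort enrolling the study's last subject the gap is 0 and there is no bias.
- A data cutoff on or before C also gives no bias.

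**What is still recorded after C.** Deaths without progression are recorded. So are deaths in the safety window, "defined as 30 days from the final administration of the trial treatment" (Protocol 10.9). In simulations with 24-month accrual and gaps of 12 or 24 months, about 3% to 12% of the deaths between C and End of Study are recordable.

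**Model (assumed).** Accrual is uniform. Time to first event is exponential with rate λ1 = ln 2 / median PFS, and post-progression survival (PPS) is exponential with rate λ2 = ln 2 / median PPS. A share q of first events are deaths without progression. True OS is

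S(t) = exp(−λ1·t) + (1 − q) · λ1/(λ1 − λ2) · [exp(−λ2·t) − exp(−λ1·t)].

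**Worked case.** Medians are PFS 6 and PPS 9 months, with q = 0.10.

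- λ1 = 0.1155 and λ2 = 0.0770 per month, so λ1/(λ1 − λ2) = 3.
- S(24) = 0.0625 + 0.90 × 3 × (0.1575 − 0.0625) = 0.319.
- Direction: subjects without progression die at q·λ1 = 0.0116 per month and progressed subjects at 0.0770, a ratio of about 6.7. After C the risk set is made up almost entirely of the first group, so the curve flattens.

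Simulation of this case used 300,000 subjects, 24-month accrual, a 12-month gap, and one month of death capture after a late progression:

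| OS at month | 18 | 24 | 30 | 36 |
|---|---|---|---|---|
| True | 0.462 | 0.319 | 0.215 | 0.142 |
| Follow-up as planned | 0.467 | 0.335 | 0.238 | 0.180 |
| All censored at C | 0.462 | 0.320 | 0.214 | not reached |
| All followed to End of Study | 0.462 | 0.319 | 0.215 | 0.142 |

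**Range.** Here q = 0.15, gaps are 6 to 24 months, and PFS/PPS medians run from 4/6 to 10/10 months. For 10/10 the rates are equal, so S(22) = exp(−1.525) × (1 + 0.85 × 1.525) = 0.50: the true median is 22 months.

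| Accrual | Excess in 24-month OS (points) | 22-month median reads |
|---|---|---|
| 12 months | 2.5 to 7 | about 26 to 28 |
| 24 months | 0.5 to 2.5 | about 23 |
| 36 to 48 months | 0.2 to 1.5 | about 22.5 |

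Across the worked-case model and its variants (accrual of 12 to 36 months), medians of 11 to 20 months move by 0 to 0.3 month.

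**Rule 2.** A subject progressing after C may have no survival status on file and then be credited with survival to the data cutoff. If so, the 6/9 case with 12-month accrual reads 0.36 to 0.38 against a true 0.30 to 0.31.

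**The case against.** The strongest reply is that the plan need not produce any visible bias, and several parts of that stand.

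- The gap is unknown for every cohort. If Cohort 2 closes last, the all-HNSCC subgroup, which comes only from Cohort 2, is unaffected. Cohort 3 opened later and may itself close last.
- Cohort 2 accrual was probably long. Enrolment was planned from the first half of 2015 (Protocol synopsis), and the amendment dated 01 November 2018 still describes the HNSCC extension as continuing. If enrolment began as planned, that is 40 to 46 months, which points to the smallest row of the table.
- SAP 7.2 names data cuts of 10 April and 30 September 2020. Their position relative to each C is not given, and a cut on or before C is safe.

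A reader might infer that the whole OS curve is inflated in every cohort. The three exceptions above rule that out. A reader might also expect a 22-month median to read 28 to 30 months; that needs 12-month accrual and no death recorded after a late progression, contrary to the 30-day window. Finally, Protocol 9.4 says that "several subjects have maintained their response and continued on treatment for over 1 year". This does not show anyone progression-free beyond C: with multi-year accrual, that year can fall well before C.

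What the reply does not remove is the rule itself. The length of follow-up depends on outcome, and the SAP neither notices nor corrects it.

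**Conclusion.** The point holds, conditionally. It applies to a cohort that closes before the study's last enrolment, and to subgroups pooling such a cohort, when the data cutoff falls after C. The late OS curve is then too high: by about 0.2 to 1.5 points at 24 months if accrual took 36 to 48 months, and by up to about 7 points if it took 12. The median is almost unmoved unless it is long. These sizes rest on assumed exponential times, uniform accrual and gaps of 6 to 24 months.

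For scale, the sampling standard error of a 24-month OS of 0.319 in 20 subjects is at least √(0.319 × 0.681 / 20) = 0.104, so the bias is smaller than the noise in any one cohort. Unlike noise, it has a fixed direction and a cheap remedy. OS is a descriptive added analysis and the response-rate decision rule is untouched, so the priority is low to moderate.

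**What to change.** In SAP 9.3, add a rule along these lines:

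> For every subject, whether or not progression has occurred, OS is administratively censored no later than the earlier of the data cutoff and the date 12 months after accrual closed in that subject's cohort. Alive status and deaths recorded after that date are listed but not analysed.

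In pooled subgroups each subject keeps their own cohort's date. Also change rule 2 so that a subject without documented survival status is censored at the last date known alive, not at the data cutoff.

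The cost is one sentence, one edited rule, and some unused late follow-up: a cohort that accrued over 12 months would have a curve ending at 12 + 12 = 24 months.

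The alternative is to follow every subject for survival to End of Study. It also removes the bias and keeps the late data. However, it needs a protocol amendment to 8.1, 10.1 and 11.7.1, with ethics and authority review and possibly renewed consent, so the SAP change is the lighter route.

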8.2 Subject Identification and Replacement of Subjects

Each subject will be assigned a unique subject identifier. This unique identifier will be on all eCRF pages. Subjects who do not receive at least one dose of tipifarnib will be replaced. Subjects who do not have post-baseline endpoint data subsequent to at least 1 dose of study drug may be replaced.

8.3 Assignment to Treatment Groups

This is a nonrandomized study. Each treatment cohort will be conducted as single arm trial. Subjects will be assigned sequentially to the available dose cohort according to tumor histology.

8.4 Removal of Subjects from Treatment or Assessment

Subjects may withdraw their consent to participate in this study at any time without prejudice. The Investigator must withdraw from the study any subject who requests to be withdrawn. A subject's participation in the study may also be discontinued at any time at the discretion of the Investigator and in accordance with his/her clinical judgment. Every effort should be made to complete, whenever possible, the tests and evaluations listed for the End of Treatment visit. The Sponsor must be notified of all subject withdrawals as soon as possible. The Sponsor also reserves the right to discontinue the study at any time for either clinical research or administrative reasons and to discontinue participation by an individual Investigator or site for poor enrolment or noncompliance.

Overall, the reasons for which the Investigator or Kura Oncology may withdraw a subject from study treatment include, but are not limited to, the following:

- Subject experiences disease progression
- Subject experiences unacceptable toxicity
- Subject experiences toxicity that is deemed by the Investigator to be no longer safe for the subject to continue therapy
- Subject requests to withdraw from the study treatment
- Subject requires or has taken medication prohibited by the protocol
- Subject is unwilling or unable to comply with the study requirements
- Subject withdraws consent to collect health information
- Subject was erroneously admitted into the study or does not meet entry criteria

- Subject is lost to follow-up
- Subject becomes pregnant

Subjects will return for an End of Treatment visit within approximately 30 days after the last administration of the study drug (or sooner if another anticancer therapy is to be initiated). If a subject fails to return for scheduled visits, a documented effort must be made to determine the reason. If the subject cannot be reached by telephone after 2 attempts, a certified letter should be sent to the subject (or the subject's legally authorized representative, if appropriate) requesting contact with the Investigator. This information should be recorded in the study records.

Prior to enrolment into the study, the Investigator or designee must explain to each subject, that the subject's protected health information obtained during the study may be shared with the study Sponsor, regulatory agencies, and IRB/IEC in order to analyze and evaluate study results. It is the Investigator's (or designee's) responsibility to obtain written permission to use protected health information per country-specific regulations, such as HIPAA in the US, from each subject, or if appropriate, the subject's legally authorized representative. If permission to use protected health information is withdrawn, it is the Investigator's responsibility to obtain a written request, to ensure that no further data will be collected from the subject and the subject will be removed from the study.

8.5 Premature Discontinuation of the Trial

This trial may be discontinued prematurely in the event of any of the following:

- New information leading to a judgment of unfavorable risk-benefit of tipifarnib becomes available, e.g. due to evidence of inefficacy of tipifarnib in HRAS mutant tumors, occurrence of significant previously unknown adverse reactions or unexpectedly high intensity or incidence of previously known adverse reactions, or other unfavorable safety findings in the HRAS mutant tumor subject population. Evidence of inefficacy may arise from this trial or from other trials and unfavorable safety findings may arise from clinical or non-clinical examinations, e.g. toxicology.
- Sponsor's decision that continuation of the trial is unjustifiable for medical or ethical reasons.
- Poor enrollment of subjects making completion of the trial within an acceptable time frame unlikely.
- Discontinuation of development of tipifarnib by the Sponsor.
- Request by a Health Authority.

Health Authorities and IRBs/IECs will be informed about the discontinuation of the trial in accordance with applicable regulations. In the case of premature discontinuation of the study, the

investigations scheduled for the End of Treatment assessment should be performed and the appropriate eCRF section completed.

8.6 Definition of End of Study

For administrative and safety reporting purposes, the end of this clinical study is defined as 12 months from enrollment of the last enrolled study subject. If the last enrolled study subject discontinues treatment within 12 months of study enrollment, the End of Study will occur no earlier than the date of the last enrolled subject's safety follow-up assessment performed approximately 30 days after treatment discontinuation (or until initiation of another anti-cancer therapy). At the time of End of Study, provisions will be made to transition all remaining study subjects who demonstrate sustained clinical benefit beyond the end of the study to other means of continued treatment with tipifarnib, including appropriate safety monitoring, e.g. single patient treatment protocol. For subjects enrolled in France and who have evidence of clinical benefit, continuation of treatment with tipifarnib may only take place in the setting of a separate study protocol. For subjects enrolled in Germany and who have evidence of clinical benefit, continuation of treatment with tipifarnib may only take place in the setting of a clinical trial or hardship program ("compassionate use") per German Drug Law (AMG).

